8.5. Treatment-Emergent Adverse Events

A TEAE is defined as an AE that occurred during the clinical trial after the first dose of IP or was present prior to dosing and exacerbates after the first dose of IP.

8.6. Serious Adverse Events

An SAE is any AE that results in any of the following outcomes:

- death;
- a life-threatening AE;
- Note: An AE is considered "life-threatening" if, in the view of either the investigator or Sponsor/designee, the subject is at immediate risk of death as a result of the AE. "Life-threatening" does not include an AE that, had it occurred in a more severe form, might have caused death.
- inpatient hospitalization or prolongation of existing hospitalization;

- Note: The term “inpatient hospitalization” refers to any inpatient admission (even if less than 24 hours). For chronic or long-term subjects, inpatient admission includes transfer within the hospital to an acute/intensive care inpatient unit. Inpatient hospitalization does not include emergency room visits; outpatient/same-day/ambulatory procedures; or admission to observation/short-stay units, rehabilitation facilities, hospice facilities, nursing homes, or clinical research/Phase 1 units.
- Note: The term “prolongation of existing hospitalization” refers to any extension of an inpatient hospitalization beyond the stay anticipated or required for the reason for the initial admission, as determined by the investigator or treating physician.
- a persistent or significant incapacity or substantial disruption of the ability to conduct normal life functions;
 - Note: A serious adverse event (SAE) specifically related to visual threat would be interpreted as any potential impairment or damage to the subject’s eyes (e.g., hemorrhage, retinal detachment, central corneal ulcer, or damage to the optic nerve).
- a congenital anomaly/birth defect; and,
- other serious (Important Medical Events) events that do not fit other outcomes, where the event may jeopardize the subject and may require medical or surgical intervention to prevent one of the outcomes listed in the SAE definition, based upon appropriate medical judgment.

8.6.1. Unexpected Adverse Event

An unexpected adverse event is defined as an AE, the nature or severity of which is not consistent with the information in the Investigator’s Brochure.

8.6.2. Reporting Serious Adverse Events

The investigator is responsible for reporting all SAEs, regardless of causality, to the Sponsor designee within 24 hours of learning of the occurrence. The paper SAE form must be sent to the study Medical Monitor, [name], at [contact]

The reporting timeframe starts when the subject signs the informed consent or assent form through 30 days after the last IP administration. At a minimum, a description of the event and the Investigator’s judgment of causality must be provided at the time of the initial report. These preliminary reports will be followed by detailed descriptions that will include copies of hospital case reports, autopsy reports, and other documents when requested and applicable.

A follow-up SAE Report must be submitted within 24 hours of the investigator receiving the follow-up information (such as information regarding complications, progression or resolution).

An SAE that is considered completely unrelated to a previously reported event should be reported separately as a new SAE.

The original copy of the SAE Report Form and the fax confirmation sheet (or email) must be kept with the source documentation at the clinical trial site.

Follow-up information should be communicated the same way, using a new SAE Report Form stating that it is a follow-up to the previously reported SAE and giving the date of the original report. The follow-up information should describe whether the event has resolved or continues, if and how it was treated, and whether the subject continued or withdrew from clinical trial participation.

The investigator and qualified site staff should institute any supplemental investigations of SAEs based on their clinical judgment of likely causative factors. This may include clinical laboratory tests not specified in the protocol, histopathologic examinations, or consultations with specialists. The Sponsor or their designee may also request the investigator to conduct supplemental assessments.

If the SAE was not previously documented in the Investigator's Brochure and is thought to be related to IP, the Sponsor or their designee may urgently require further information from the investigator for regulatory authority reporting. The Sponsor may need to issue an investigator Notification to inform all investigators involved in any clinical trial with the same drug that this SAE has been reported.

8.6.3. Follow-up of Adverse Events

All AEs will be followed until stabilization/resolution or until clinical database lock. AEs are to be reported to the IRB in accordance with IRB policy.

All SAEs will undergo active follow-up until resolved or the event becomes chronic or stable. Follow-up data for SAEs obtained after clinical database lock will be incorporated into the safety database.

8.6.4. Reporting Serious Adverse Events to Regulatory Health Authorities/ Institutional Review Boards/Research Ethics Boards/Independent Ethics Committees

The investigator is responsible for following all local regulations for the reporting of safety information, including the reporting of SAEs to their local IRB/REB/IEC.

The investigator must promptly report to his or her local IRB/REB/IEC all unanticipated problems involving risks to subjects. This includes death from any cause and all serious adverse events reasonably or possibly associated with the use of IP.

The Sponsor or their designee is responsible for appropriate reporting of relevant AEs, suspected unexpected serious adverse reactions (SUSARs) involving IP, to all regulatory authorities.

In addition, the Sponsor or designee will be responsible for the submission of safety letters (e.g., SUSARs) to the central IRB/REB/IEC and to participating investigators of all SUSARs involving IP according to applicable regulations.

After termination of the clinical trial (determined as last subject, last visit), any unexpected safety issue that changes the risk-benefit analysis and is likely to have an impact on the subjects

who have participated in it, will be reported by the Sponsor as soon as possible to the competent authority (ies) concerned together with proposed actions.

8.7. Reporting Pregnancies

Pregnancies for women will be reported from the time the subject signs the informed consent form through final clinical trial visit or 30 days after the last IP administration, whichever is later. Males will report pregnancy of their partners through 90 days after the last IP administration.

Subjects who become pregnant will be withdrawn from the clinical trial. The pregnancy should be followed up to determine outcome, including spontaneous or voluntary termination, details of the birth, and the presence or absence of any birth defects, congenital abnormalities, or maternal and/or newborn complications.

Pregnancy should be recorded on a subject's source documents and a Pregnancy Notification and Outcome Form and reported using the same procedure for reporting SAEs detailed in Section 8.6.2. A pregnancy, by itself, is not an SAE. Pregnancy follow-up should also be recorded and should include an assessment of the possible relationship to the IP of any pregnancy outcome. Any pregnancy-related SAE (e.g., spontaneous abortion, birth defect) or any other SAE experienced during pregnancy must be recorded on a separate SAE Report Form and reported per SAE reporting procedures in Section 8.6.2.

9. STATISTICS HYPOTHESES AND METHODS OF ANALYSES

9.1. Clinical Trial Populations

9.1.1. Intent-to-Treat (ITT)

The Intent-to-Treat (ITT) population consists of all subjects who are enrolled and receive the IP. All data will be included, and no subjects will be excluded because of protocol violations.

9.1.2. Per-Protocol Population

The Per-Protocol (PP) population is a subset of the ITT population and includes the subjects who completed the trial with no major protocol violations.

9.1.3. Safety Population

The safety population includes all enrolled subjects who received the test article. The safety population will be analyzed as treated and will be used for the safety analyses. No data will be excluded for any reason.

9.2. Statistical Analysis

9.2.1. General Considerations

Quantitative variables will be summarized descriptively using number of subjects (n), mean, standard deviation, median, minimum, and maximum. Qualitative variables will be summarized using counts and percentages.

All analyses will be two-sided at a significance level of 0.05. The 95% confidence intervals will be provided where appropriate.

The SAP will serve as the final determinant of the statistical procedures, notwithstanding anything herein.

9.2.2. General Imputation Methods

Every attempt will be made to capture all clinical trial data. The method on how to handle the complete and/or partial missing data in the adverse events and medications will be addressed in these individual analysis sections of the SAP.

9.2.3. Multiplicity Consideration

Only one hypothesis will be tested. No multiplicity adjustment will be done in this clinical trial.

9.2.4. Demographic and Baseline Medical History

The demographic and baseline medical history data, obtained at screening, will be summarized descriptively. For quantitative variables, the summaries will include the number of observations, mean, standard deviation, median, minimum, and maximum. Qualitative variables will be summarized using counts and percentages.

9.2.5. Primary Endpoint Analyses

Safety endpoints will be summarized descriptively. Safety endpoints include:

- Slit-lamp evaluation
- Dilated ophthalmoscopy
- Adverse event (AE) query (reported, elicited, and observed)

Adverse events will be summarized descriptively. Frequencies and percentages will be provided per treatment group of subjects with treatment-emergent adverse events (TEAEs), serious TEAEs, and TEAEs causing premature discontinuation. An adverse event is treatment-emergent if it occurs after the first dose of investigational treatment. Furthermore, frequencies will be given of subjects with TEAEs by system organ class, by system organ class and preferred term, by system organ class, preferred term and maximal severity, by system organ class, preferred

term and strongest relationship, and by system organ class, preferred term, maximal severity, and strongest relationship.

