Assessment	Visit 1 (V1)	Visit 2 (V2)	Visit 3 (V3)	Visit 4 (V4)	Visit 5 (V5)	Visit 6 (V6)	Visit 7 (V7)	Visit 8 (V8)	Visit 9 (V9)	Visit 10 (V10)
	Screening Visit A	Screening Visit B Week 0	Day 4 ¹	Week 2 ²	Week 4 ²	Week 6 ³	Week 8 ³	Week 10 ³	Week 12 ³	Week 16 ³
Informed consent	X									
Eligibility criteria	X									
Demography, medical and ocular history	X									
Best Corrected Visual Acuity	X ⁴	X ^{4,6}	X ⁴		X ⁴		X ⁴		X ⁴	X ⁴
Low Luminance Visual Acuity	X ⁴	X ^{4,6}	X ⁴		X ⁴		X ⁴		X ⁴	X ⁴
Full ophthalmic exam, including intraocular pressure, slit lamp, and dilated funduscopy	X ⁴		X ⁴		X ⁴		X ⁴		X ⁴	X ⁴
Wide-field Color Fundus Photography and Autofluorescence	X ⁴								X ⁴	X ⁴
Macular SD-OCT (Spectral Domain Optical Coherence Tomography)	X ⁴				X ⁷		X ⁷		X ⁴	X ⁴
Dark-Adapted Chromatic (DAC) Perimetry	X ⁷	X ^{6,7}	X ⁷		X ⁷		X ⁷		X ⁷	X ⁷
Macular Integrity Assessment (MAIA) Microperimetry	X ⁷	X ^{6,7}	X ⁷		X ⁷		X ⁷		X ⁷	X ⁷
Full field electroretinography	X ⁴								X ⁴	
Cohort A (Monthly ADX-2191 injection)										
Corneal Slit Lamp Safety Exam		X ⁷								
Urine Pregnancy Test		X			X		X			
Intravitreal injection of ADX-2191		X ^{5,7}			X ^{5,7}		X ^{5,7}			
Concomitant medications	X	X	X		X		X		X	X
Adverse events	X	X	X		X		X		X	X
Cohort B (Bimonthly ADX-2191 injection)										
Corneal Slit Lamp Safety Exam		X ⁷		X ⁷		X ⁷		X ⁷		
Urine Pregnancy Test		X		X	X	X	X	X		
Intravitreal injection of ADX-2191		X ^{5,7}		X ^{5,7}	X ^{5,7}	X ^{5,7}	X ^{5,7}	X ^{5,7}		
Concomitant medications	X	X	X	X	X	X	X	X	X	X
Adverse events	X	X	X	X	X	X	X	X	X	X

¹: Visit window +/- two days²: Visit window +/- three days³: Visit window +/- five days⁴: Bilateral evaluation⁵: Injection to be performed after all other assessments have been performed.⁶: Results from Screening Visit B (V2) will be used for quantitative study analysis purposes.

Investigator may repeat any tests of Screening Visit B on a separate unscheduled visit if a difference in results is observed from Screening Visit A, as per investigator assessment

⁷: Study eye only

TABLE OF CONTENTS

INVESTIGATOR STATEMENT2

SUMMARY OF CHANGES3

SYNOPSIS4

LIST OF ABBREVIATIONS AND DEFINITION OF TERMS12

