6.7. Ophthalmic Examinations

6.7.1. Best-Corrected Visual Acuity

BCVA will be collected at Screening Visit A (V1), Screening Visit B (V2), and Visits V3, V5, V7, V9, and V10. The BCVA will be measured using ETDRS chart by masked technicians at a standard photopic light level of at least 85 cd/m². Both eyes will be examined at all time points.

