8.4. Assessment of Causality and Severity

For each AE recorded, the investigator will make an assessment of causality and severity as follows:

1. Relationship to IP: The investigator must assess whether they consider an AE to be drug-related. In assessing this relationship, the investigator must use information about the drug as outlined in the Investigator's Brochure, the subject's pre-existent medical conditions/concurrent medication, and chronology of the event relative to drug administration. The following definitions will be used:
 - Definitely Related
 - Probably Related
 - Possibly Related
 - Unlikely to be related
 - Not Related

For regulatory authority reporting, only "related," or "not related" classification will be used. AEs identified as definitely, probably, or possibly, will be classified as "related." Those AEs identified as unlikely, or not related, will be classified as "not related."

2. Event Severity: The investigator will be asked to use their medical judgment to assess the severity of the AE.
3. The following are guidelines to be used by the investigator to judge the event severity of an AE:
 - Mild (Grade I) - awareness of sign or symptom, but easily tolerated
 - Moderate (Grade II) - discomfort enough to cause interference with usual activity

- Severe (Grade III) - incapacitating with inability to work or perform usual activity
 - Very Severe (Grade IV) – Vision or life-threatening; urgent intervention indicated
 - Death (Grade V) – death of subject
4. Expectedness: The expectedness of an AE should be determined based on upon existing safety information about the IP using the following explanations:
- *Unexpected*: an AE that is not listed in the IB or is not listed at the specificity or severity that has been observed.
 - *Expected*: an AE that is listed in the IB at the specificity and severity that has been observed.
 - *Not applicable*: an AE unrelated to the IP.
 - AE events that are mentioned in the IB as occurring with a class of products or as anticipated from the pharmacological/mechanical (or other) properties of the product but are not specifically mentioned as occurring with the particular product under investigation, are to be considered unexpected.
 - The investigator should initially classify the expectedness of an AE, but the final classification is subject to the determination of the Sponsor's Medical Monitor.
5. Duration: Start and end dates and times, or if continuing.

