9.2.6. Secondary Endpoint Analyses

Secondary endpoints will be analyzed to evaluate for change from Screening Visit B (Visit 2) to the level at Week 16 (Visit 10). Change from Screening level will be the dependent variable. The secondary endpoints include letters of BCVA or LLVA, improvement in visual field area and microperimetry, and increase in dark-adapted flash b-wave amplitudes.

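### Visual acuity is not a named safety endpoint, so acuity loss during dosing that recovers by Week 16 has no specified count or size in letters

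*Combined protocol and SAP*

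**What the plan says.** Section 2.2.1 makes safety and tolerability the primary endpoint. Section 9.2.5 then states: "Safety endpoints will be summarized descriptively. Safety endpoints include" three items, namely slit-lamp evaluation, dilated ophthalmoscopy and "Adverse event (AE) query (reported, elicited, and observed". Treatment-emergent adverse events are tabulated by treatment group, system organ class, preferred term, maximal severity and relationship.

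Acuity is a secondary endpoint (section 2.2.2). Section 9.2.6 sets its analysis: "Secondary endpoints will be analyzed to evaluate for change from Screening Visit B (Visit 2) to the level at Week 16 (Visit 10". Section 6.7.1 collects much more: "BCVA will be collected at Screening Visit A (V1), Screening Visit B (V2), and Visits V3, V5, V7, V9, and V10", in both eyes each time. On visits with both testing and dosing, a footnote to Table 1 puts the dose last: "Injection to be performed after all other assessments have been performed".

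Four other places bear on the point:

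- Section 8.1 tells investigators not to report abnormal findings as adverse events unless they come with signs and symptoms, cause discontinuation or are judged clinically relevant.
- Section 8.6 explains that a serious event "specifically related to visual threat would be interpreted as any potential impairment or damage" to the eyes, and Grade IV in section 8.4 covers "Vision or life-threatening; urgent intervention indicated". Section 8.3 applies CTCAE grading first and uses the section 8.4 scale only where CTCAE lists no grade.
- Section 9.2.1 gives standard summary statistics for quantitative variables, without naming visits or eyes.
- Sections 9.2.1 and 9.2.8 give the SAP the final word. It is to be finalized before database lock, and no SAP text is in the document.

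**The concern.** The primary question is whether repeated intravitreal methotrexate can be given safely. Section 1.2.1 names keratopathy as a known risk. The drug could cost a patient letters while dosing continues and give them back once it stops. The one specified acuity comparison uses the visit furthest from any dose, so it is the least able to show this. Visits 3 to 9, during and soon after dosing, have acuity readings but no stated analysis.

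If acuity fell and recovered, the primary result would still report visible injury on slit-lamp or funduscopy and any loss recorded as an adverse event. It would not state how many study eyes lost letters, or how many letters they lost. Whether a measured drop entered the result at all could rest on investigator judgment in an open-label study, with no letter threshold in the adverse event, serious event or withdrawal text. The only acuity-based removal rule is no light perception (section 4.3).

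**Working it through.** The plan states no figure on this point, so there is nothing to reproduce. The check covers timing, coverage, noise and what 8 eyes can show.

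**Time since the latest dose.** From Table 1, nominal dose days are 0, 28 and 56 in Cohort A, and 0, 14, 28, 42, 56 and 70 in Cohort B. Post-dose BCVA falls on days 4, 28, 56, 84 and 112. Readings at Visits 5 and 7 come before that day's injection. Days since the latest earlier dose:

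| Visit (day) | Cohort A | Cohort B |
|---|---|---|
| V3 (4) | 4 − 0 = 4 | 4 − 0 = 4 |
| V5 (28) | 28 − 0 = 28 | 28 − 14 = 14 |
| V7 (56) | 56 − 28 = 28 | 56 − 42 = 14 |
| V9 (84) | 84 − 56 = 28 | 84 − 70 = 14 |
| V10 (112) | 112 − 56 = 56 | 112 − 70 = 42 |

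Week 16 has the longest gap in both cohorts. The cohorts match only at V3, when each has had one identical dose.

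**Coverage.** One of five post-dose visits has a specified acuity analysis. With 8 completers there are 8 × 5 = 40 post-dose study-eye readings, and 8 × 4 = 32 have none.

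**Noise in a letter-loss count.** The documents give no SD for between-visit change, so 3, 5 and 7 letters are assumed. Letter thresholds of 15 and 10 are also assumed. For each SD, 2,000,000 stable eyes were simulated with normal readings rounded to whole letters, reading SD = change SD/√2, a shared V2 baseline, and the lowest change over five visits taken. With p the per-eye chance of a false drop, the chance of at least one among 8 eyes is 1 − (1 − p)^8:

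| SD of change | p, loss ≥ 15 | At least 1 of 8 | p, loss ≥ 10 | At least 1 of 8 |
|---|---|---|---|---|
| 3 | < 0.0001 | < 0.1% | 0.0037 | 2.9% |
| 5 | 0.0084 | 6.5% | 0.1038 | 58% |
| 7 | 0.0726 | 45% | 0.2634 | 91% |

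An unreferenced count could therefore mislead, and the 10-letter count more so.

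**Noise reference from V1 to V2.** Eight pre-dose changes give an SD on 7 degrees of freedom. Its 95% interval runs from √(7/16.01) = 0.66 to √(7/1.690) = 2.04 times the estimate.

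**What 8 eyes can show.** If the true risk of such a loss were 10% to 30% (assumed), the chance of at least one case would be 1 − 0.9^8 = 57% to 1 − 0.7^8 = 94%. With 0 of 8 affected, the exact two-sided 95% upper limit is 1 − 0.025^(1/8) = 36.9%. Between cohorts of 4, two-sided Fisher p is 2/70 = 0.029 for 4/4 versus 0/4, and 2 × 4/56 = 0.14 for 3/4 versus 0/4. Only complete separation falls below 0.05.

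**The case against.** The strongest reply is that this argues from silence. The protocol leaves detailed analyses to an SAP that overrides it, and by-visit tables are ordinary SAP content. The text of 9.2.5 introduces its list with a word that need not be exhaustive, and the list also omits intraocular pressure, which is measured at every full examination. Section 9.2.6 is visibly not a complete specification: it asks for a V2-to-V10 change in the electroretinogram, which is collected only at V1 and V9, and it leaves out OCT. Section 9.2.1 could be read as covering BCVA at every visit, and a visit's minimum change is that visit's worst loss.

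The adverse event route is also substantial. Events are elicited as well as reported and are assessed at each visit. The synopsis promises by-subject listings and narratives for serious events. Nominally, V3 to V9 all fall within 30 days of a dose, inside either stated collection window. CTCAE grades may convey some size of acuity loss; the documents do not allow that to be checked. Finally, a letter-loss count in 8 eyes is noisy.

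Most of this is fair, and it limits the point to analysis rather than data collection. It does not remove it. None of these provisions specifies acuity by visit, by eye or in letters lost, and section 8.1 makes conversion of a measured drop into an adverse event conditional. The noise calls for a reference alongside the count; it does not justify leaving the readings unanalyzed.

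**Conclusion.** The concern holds. As written, the protocol names no acuity measure among its safety endpoints and specifies an acuity analysis at one of five post-dose visits, the one furthest from dosing. Loss that recovers by Week 16 can reach the primary result as an adverse event or a visible sign, but with no specified count of eyes or size in letters.

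The point is worth acting on but is not a fatal flaw, because the data are collected and the adverse event route covers part of the risk. The timing and coverage results rest on nominal visit days and 8 completers. The noise figures rest on assumed SDs and thresholds. Confidence is moderate, chiefly because the SAP may already include the missing summaries.

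**What to change.** Add BCVA to the safety endpoints in section 9.2.5, or specify it as such in the SAP, before outcome data are reviewed:

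- Summarize change from V2 at V3, V5, V7, V9 and V10, by cohort and separately for study and fellow eyes.
- Report each subject's worst post-dose change, with a by-subject listing.
- Count study eyes losing at least 15 letters (main) and at least 10 letters (supporting) at any post-dose visit. Fix the thresholds in advance; the documents give none.
- Show the same counts in fellow eyes as a noise reference, noting that the fellow eye is the better-seeing one and may vary less.
- Show the V1-to-V2 change in study eyes, which measures noise in the eyes of interest. It is imprecise with 8 eyes and may understate noise, because footnote 6 to Table 1 says "Investigator may repeat any tests of Screening Visit B on a separate unscheduled visit if a difference in results is observed" from Screening Visit A.
- State that cohort results are descriptive only. State also that loss recovering within 28 days (Cohort A) or 14 days (Cohort B) of a later dose stays unseen, since only the first dose has an early acuity visit.

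Leave the Week 16 efficacy analysis unchanged.

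The cost is a short addition to section 9.2.5 or the SAP and one or two tables from data already collected, with no new visits or procedures. The downside is that the safety result may look slightly less favourable and some counted drops will be chance. The two noise references help to judge those but cannot remove them.

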1.2. Potential Risks and Benefits

1.2.1. Potential Risks

General risks for intravitreal injection include infection, hemorrhage; precipitated angle closures; elevated intraocular pressure (IOP) with perfusion compromise; wound leak and hypotony; anaphylactic reaction to either the agent or periprocedural materials.

In addition, known risks associated with use of intravitreal methotrexate include:

- keratopathy. Therefore, all subjects will be recommended to use lubricating eye drops at a minimum of four times a day during the study period.

- mild conjunctival hyperemia (“red eye”) and slight pain at injection site. This hyperemia and/or slight pain is seen in almost all eyes receiving methotrexate and resolves within several hours.

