6.7.7. Full Ophthalmic Clinical Examination

Routine full ophthalmic, dilated exams, including intraocular pressure measurement, slit lamp examination, and dilated funduscopy will be performed on Screening Visit A (V1) and Visits V3, V5, V7, V9, V10. Both eyes will be examined at all time points. The full ophthalmic exam will also serve as the corneal safety assessment on days when a full ophthalmic exam is done prior to an intravitreal injection.

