8.1. Adverse Event

An AE is any untoward medical occurrence in a patient administered an IP, which does not necessarily have a causal relationship with the IP treatment. Therefore, an AE can be any unfavorable and unintended sign, symptom, or disease temporally associated with the use of the IP, whether or not it is considered related to the IP.

Abnormal investigational findings (i.e., physical exam) should not be reported as AEs unless they are associated with clinical signs and symptoms, lead to treatment discontinuation, or are otherwise considered clinically relevant by the investigator. In cases of surgical or diagnostic procedures, the condition/illness leading to such a procedure is considered as the AE rather than the procedure itself. In case of a fatality, the cause of death is considered as the AE, and the death is considered as its outcome.

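### Section 9.2.5 drops the worsening limb of the Section 8.5 TEAE definition and does not name IOP among the safety endpoints

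*Combined protocol and SAP*

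**What the plan says.** **TEAE definition.** Section 8.5 has two limbs: an AE that occurs after the first dose, or one that "was present prior to dosing and exacerbates after the first dose of IP". Section 9.2.5 gives one limb: "An adverse event is treatment-emergent if it occurs after the first dose of investigational treatment". Section 9.2.5 then specifies counts of subjects with TEAEs, serious TEAEs and TEAEs leading to discontinuation, followed by breakdowns by system organ class, preferred term, maximal severity and strongest relationship.

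**Safety endpoints.** Section 9.2.5 opens its list with "Safety endpoints will be summarized descriptively. Safety endpoints include" and names slit-lamp evaluation, dilated ophthalmoscopy and the AE query. IOP is not on the list. Section 6.7.7 describes the examination that supplies the first two: "Routine full ophthalmic, dilated exams, including intraocular pressure measurement, slit lamp examination, and dilated funduscopy will be performed". Table 1 and Section 6.7.7 place this examination, in both eyes, at V1, V3, V5, V7, V9 and V10. Section 1.2.1 lists among the risks of intravitreal injection "elevated intraocular pressure (IOP) with perfusion compromise".

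**When a finding becomes an AE.** Section 8.1 says: "Abnormal investigational findings (i.e., physical exam) should not be reported as AEs unless they are associated with clinical signs and symptoms". It goes on to add findings that "lead to treatment discontinuation, or are otherwise considered clinically relevant by the investigator".

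**Other displays.** The synopsis provides for all AEs from Visit 1 to Visit 10 to be listed by subject and tabulated, whatever their TEAE status.

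**The concern.** The two TEAE definitions are both current text of the same protocol, and the narrower one stands in the section from which the tables will be programmed. Where they differ, the narrower one can only lower the count. Read literally, an event that began before dosing and became severe or serious afterwards would be missing from the severity and serious-TEAE tables, which are where a reader looks for harm.

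On IOP, the examination has three named components. Two are carried into the safety endpoints, and the third, which relates to a listed risk of the procedure, is not. The values are collected, but the plan does not say how they will be shown.

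The trial is open-label, so results will be visible as they accrue. Definitions that decide what enters the primary tables are best settled beforehand.

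**Working it through.** The documents give no figure on this point to reproduce. The check is a comparison of text, with simple arithmetic for scale.

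**1. Which events do the two definitions treat differently?**

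| Event | Section 8.5 | Section 9.2.5, read literally |
|---|---|---|
| Starts after the first dose | TEAE | TEAE |
| Condition present before V1, worsens after dosing (an AE by implication of 8.2) | TEAE | TEAE if the worsening is recorded as a post-dose event |
| AE with onset between V1 and the V2 injection, worsens after dosing | TEAE | Not a TEAE if it keeps its pre-dose start date |
| AE with onset between V1 and V2, does not worsen | Not a TEAE | Not a TEAE |

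The clear disagreement is the third row. It can occur: Section 8.3 records AEs from consent, and Table 1 puts consent at V1 and the first injection at V2. Section 8.3 asks for changes in severity to be assessed at each visit, and Section 8.4 records start and end dates for each event. Neither says that a worsening must be entered as a new event, so the original start date can stand.

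**2. Size of one such case.** Inputs: 4 subjects per cohort and 8 in all (Section 3.1).

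- Change in the incidence of the affected term = 100/n: 100/4 = 25 points in a cohort, 100/8 = 12.5 points pooled.
- Exact (Clopper-Pearson) 95% limits for that term:

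| n | 0 events | 1 event |
|---|---|---|
| 4 | 0 to 60.2% | 0.6 to 80.6% |
| 8 | 0 to 36.9% | 0.3 to 52.7% |

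The overall TEAE incidence moves only if the subject has no other TEAE. Section 1.2.1 says that brief redness or slight injection-site pain is seen in almost all treated eyes. If sites record these as AEs (an assumption), overall incidence may already be near 100%, and only individual term rows would change.

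**3. IOP readings.** There are six scheduled readings per eye: one before dosing (V1) and five after the first dose (V3, V5, V7, V9, V10). At V2 the schedule has only the corneal slit-lamp examination, so V1 is the only scheduled pre-dose IOP. With 8 subjects and two eyes this gives 8 × 2 × 6 = 96 readings, none with a named summary.

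**4. What those readings can show.** Table 1 puts the injection after all other assessments. The V5 and V7 readings therefore precede that day's injection, and no IOP reading is scheduled at V4, V6 or V8. The nominally closest reading after any injection is Day 4, after the first. A by-visit summary would show sustained change, not acute post-injection spikes.

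**The case against.** **The strong reading fails.** A reader might infer that worsened events and IOP rises vanish from the safety results, or that the whole primary analysis consists of TEAE tables. The documents support neither. Slit-lamp and ophthalmoscopy findings are to be summarised in their own right, so corneal worsening can show there under either definition. The synopsis tabulates every AE from V1 to V10. Under Section 8.1 an IOP rise judged clinically relevant is an AE even without symptoms and, after the first dose, a TEAE under both definitions.

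All of this stands, and it limits the consequence. It does not remove it: a tabulation of all AEs does not identify which pre-dose events worsened on treatment, and it does not summarise IOP values or rises below the investigator's judgement of relevance.

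**The gap is narrow.** A condition present before V1 that worsens after dosing can count as a post-dose AE, and Section 3.5.2 excludes severe dry eye and other significant corneal disease. This too is right. The remaining case is an AE that arises in the interval from V1 to V2, in about eight subjects, and it may not occur at all.

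**The list is not closed, and the SAP governs.** The endpoint list is introduced by the word *include*, and Section 9.2.1 says that quantitative variables will be summarised descriptively. Sections 9.2.1 and 9.2.8 let a later SAP override the protocol. The SAP may therefore settle both points. However, the document reviewed contains no separate SAP text, the SAP need only be final before database lock, and Section 9.2.2 expressly defers only the handling of missing AE and medication data. The general rule on quantitative variables names neither IOP nor its baseline.

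**Conclusion.** The point holds in limited form. Section 9.2.5 conflicts with Section 8.5, and an AE with recorded onset between V1 and the V2 injection that worsens after dosing may be left out of the TEAE tables. Whether it is left out depends on 9.2.5 being followed literally and on the event keeping its pre-dose start date. Each such subject is worth 25 percentage points on the affected term in a cohort of 4. How many there will be cannot be estimated from the documents.

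IOP values, and rises not judged clinically relevant under Section 8.1, have no named summary although the data are collected. Clinically relevant rises are covered as AEs.

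The textual mismatch is certain, but its effect on the results is possible rather than certain. It is worth correcting because safety is the primary endpoint, the groups are very small and the correction costs almost nothing.

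**What to change.** 1. Replace the TEAE sentence in Section 9.2.5 with the Section 8.5 definition: onset after the first dose, or present before dosing and exacerbated after it. An event is then classified the same way whether the site records the worsening as a new event or as a change in an existing one.
2. Add IOP to the safety endpoints in Section 9.2.5: value and change from V1 by visit, for study eye and fellow eye, and the maximum post-dose IOP for each subject. State with the table that V1 is the only scheduled pre-dose reading and that V5 and V7 are taken before that day's injection, so acute post-injection spikes are not captured.
3. Carry both into the SAP, since it overrides the protocol.

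Cost: two sentences and a few tables, with no new data collection. TEAE counts may come out slightly less favourable.
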